### **Sample size calculations**

Sample size calculations were derived using Stata 16 and are based on the Self-Report Delinquency Scale (Smith and McVie, 2003). This measure has 18 two-part questions that measure the number of different offences committed, and the volume of offences committed

over a fixed period. We are interested in the latter outcome over a six-month period. The scale has good psychometric properties (Fonagy et al., 2018, Humayun et al., 2017) and correlates well with official police charges ( $R = 0.95$ ; (McAra and McVie, 2007)).

We have used an effect size difference of 0.25 as an important difference; this equates to a difference in volume of offences of circa 12% over a 6-month period, similar effects as found in other psychologically focussed interventions to reduce recidivism in adolescent populations (Hodgkinson et al., 2021). To detect this difference or greater, using a two-sided test, alpha of 0.05 and power at 80% requires 506 young people to be followed-up at our primary endpoint, 6-months post-randomisation, 253 in each group. There is no reliable literature on pre- and post-test correlations for the SRDS, so we have erred on the side of caution and not accounted for this in the sample size calculation as an incorrect assumption increases the risk of an under-powered trial. If we take a potential loss to follow-up of 10%, similar to attrition found in our other studies of young people (Coulton S et al., 2023), this inflates the required baseline sample to 562. We have 80 potential interventionists, 40 randomised to each arm. Each interventionist can manage a harmonic mean of 10 young people through the course of the study. To achieve our target, we would need to have at least 56 of these interventionists participating throughout the trial, 28 in each arm, thus allowing for a potential loss of interventionists of 24, 30% of those available.

Assuming only 80% of young people approached consent to take part, as found in similar studies (Coulton S et al., 2023), means we would need to approach 702 young people, over the recruitment period. Allowing for a slower start of 20/ per month recruited over the first three months, means 36 will need to be recruited in each month between January 2024 and February 2025, allowing for a six-month follow-up for the interim report submitted in September 2025.

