## **Intervention**

The intervention, RBT, involves a model of practice that aims to avoid stigmatising and criminalisation of young people through the identification and formulation of a sequence of

interventions that respond to the childhood trauma experienced by the young people. Greater detail on the theoretical framework and the intervention approach is available here: <https://www.trmacademy.com/#theModel> and the hypothesised theory of change is articulated in figure 1. The intervention builds on work already delivered in youth justice services in Bridgend over the past 18 months, to include a population of young people in other services: Edge of Care, Children's Services, Youth Development, and Early Help – who may be starting to display challenging behaviour as a response to their trauma.

Practitioners are randomly allocated to receive training or not using a secure on-line randomisation service employing a minimisation algorithm which means staff are allocated to ensure balance between service and specialisation. 50% are allocated to RBT training and 50% continuing with BAU. The initial training is delivered to 35-40 staff members over 3-days by specialist trainers from the Trauma Recovery Model Academy. Trainers are experienced practitioners; social workers, clinical psychologists and youth workers who have developed and delivered the RBT intervention for many years across several different services working with young people. Training aids practitioners to understand the impact of prior trauma on the young person's behaviour, the development of strategies to reduce the behavioural consequences of trauma, building relationships and communication, the principles of case management and how to employ evidence-based interventions to promote positive development, and ensuring trauma histories are embedded in the case management process.

Up to ten senior members of staff, consisting of managers for each service and those currently responsible for core assessment of need on referral, will receive an additional two-day training with the aim of becoming trauma leads and champions within their departments. These staff will receive monthly mentoring throughout the project and shadowing from other similar services in Wales. These trauma leads will take responsibility for the core assessment of need, case formulation meetings and embedding trauma informed practice within services.

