Level two allocation involves the randomisation of young people to RBT or BAU. This will be conducted by research staff, using a secure, on-line randomisation service (Sealed Envelope Ltd). after informed consent has been taken and the baseline assessment completed and before any trauma screening has been conducted. The allocation will involve an equal probability of receiving RBT or BAU and will employ random permuted blocks of variable size (4, 6 or 8) with a random block seeded throughout. Randomisation will be conducted by research staff using a secure, independent randomisation service, Sealed Envelope Ltd. Randomisation will be stratified by service (youth justice, edge of care, youth development, early help, children's services), sex (male, female), and age group (<15 years, 15 years or more). Stratification variables have been chosen to ensure allocation is balanced across services, sex, and age as some workers specialise in working with older or younger males and females. A full quality assurance AUDIT trail will be kept of all allocations and research staff will not be able to see future allocations. The allocated group will be relayed back to delivery staff in the services who will decide which staff member, matching their allocated intervention or control group, a young person should be assigned to.

It is not possible to blind young people or staff to their allocated group although follow-up at months 6 and 12 will be conducted by researchers blind to allocation. Follow-up questionnaires are completed by participants and are the same for both groups, the questionnaires collect no details on what group the participant was allocated to.

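### The stated equivalence of 0.25 SD to about 12% of offence volume needs an SD of 0.48 times the mean, which cannot hold if more than about 19% of participants report no offences

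*Protocol*

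**What the plan says.** In Sample size calculations the protocol states "We have used an effect size difference of 0.25 as an important difference" and continues that "this equates to a difference in volume of offences of circa 12% over a 6-month period", citing a systematic review of resilience interventions. The SAP repeats this in Sample size calculations overview. Neither shows the conversion.

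The outcome used for the calculation is the volume of offences, not the number of different offence types: "We are interested in the latter outcome over a six-month period". For the target effect, a "two-sided test, alpha of 0.05 and power at 80% requires 506 young people to be followed-up at our primary endpoint", 253 per arm, or 562 after allowing for 10% loss. On the pre/post correlation the authors write that "we have erred on the side of caution and not accounted for this in the sample size calculation". The sample size tables in both documents list only the standardised effect of 0.25, with correlations marked not applicable.

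The primary result is a mean difference with a 95% confidence interval from a linear model adjusted for baseline SRDS, sex, age group and service (SAP, Primary outcome analysis).

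**The concern.** A standardised effect becomes a percentage of the mean only through the ratio SD/mean (the coefficient of variation, CV). By giving both figures the plan fixes that ratio, yet it reports no SRDS mean, SD or share of participants with no offences. The implied value is very small for an offence count in this population.

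The 12% is the only meaning on the offence scale that the plan gives to its important difference, and the primary result will be reported on that scale. If 0.25 SD is in truth a much larger percentage, readers will take the trial to have 80% power for a 12% reduction when it does not, and may take a null result as evidence against one.

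**Working it through.** **Inputs.** From Sample size calculations (both documents): effect 0.25 SD, stated equivalent about 12%, two-sided alpha 0.05, power 80%, 506 analysed. From Protocol, Randomisation: "The allocation will involve an equal probability of receiving RBT or BAU", so 253 per arm. SRDS mean, SD and share of zeros: not given, so CV is an assumption shown as a range.

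**1. The plan's own figure.** A two-sample t-test for d = 0.25 needs 252.1 per arm, rounded up to 253, or 506 in total; power at 253 per arm is 80%. Allowing for 10% loss, 506/0.9 = 562.2, against 562 stated. The sample size reproduces.

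**2. The implied CV.** If 0.25 × SD = 0.12 × mean, then SD/mean = 0.12/0.25 = 0.48.

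**3. Ceiling on zeros.** Let p0 be the share with zero and M the mean among the rest. The overall mean is (1 − p0)M, and the mean square is at least (1 − p0)M². Hence CV² ≥ 1/(1 − p0) − 1 = p0/(1 − p0), which gives p0 ≤ CV²/(1 + CV²). With CV = 0.48, p0 ≤ 0.2304/1.2304 = 18.7%. If the rounded 12% covers 11.5% to 12.5%, CV is 0.46 to 0.50 and the ceiling is 17.5% to 20.0%. Equality needs every participant with any offence to report the same number, so real spread lowers the ceiling. The SAP scores the outcome as a sum of positive endorsements; that is also non-negative, so the same bound applies.

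**4. Poisson check.** For a Poisson count CV = 1/√mean, so CV = 0.48 needs a mean of 1/0.2304 = 4.3 offences in six months. Overdispersion would need a higher mean.

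**5. Plausibility from the documents.** Protocol, Participants, admits all consenting referrals aged 10 to 21 to five services, with no offending requirement. Protocol, Intervention, describes Early Help as practical advice and support and Youth Development as signposting and mentoring, and describes young people in the services other than youth justice as those "who may be starting to display challenging behaviour as a response to their trauma". A zero share below 19% is hard to reconcile with that.

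**6. Consequence over assumed CVs.** The percentage matching 0.25 SD is 25 × CV. Power for a true 12% difference is the t-test power at d = 0.12/CV with 253 per arm, unadjusted.

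| Assumed CV | 0.25 SD as % of mean | Power for 12% |
|---|---|---|
| 0.48 | 12% | 80% |
| 0.75 | 19% | 44% |
| 1.0 | 25% | 27% |
| 1.5 | 38% | 15% |
| 2.0 | 50% | 10% |

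Using the bound alone (the smallest possible CV), the best unadjusted power for 12% is 77% at 20% zeros, 54% at 30% and 27% at 50%.

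**7. Baseline adjustment.** With pre/post correlation r, the residual SD is SD × √(1 − r²). At CV 1.0, power for 12% becomes 34% (r = 0.5) or 47% (r = 0.7); at CV 0.75 and r = 0.7 it is 71%. Power of 80% for 12% holds up to CV = 0.48/√(1 − r²), which is 0.55 or 0.67, or at most 23.5% or 31% zeros. Both correlations are assumptions.

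**The case against.** A reader might infer flatly that the trial is not powered for a 12% reduction. The documents do not support that. It follows only if the CV is above 0.48, and they give no SRDS mean, SD or zero share. The description of the services makes more than 19% zeros likely but does not measure it. The 38.5% re-offending rate in Study rationale and background is a national figure for offenders, not an SRDS result, so it cannot settle the matter. The planned adjustment for baseline SRDS also raises power above the unadjusted figures. These points stand, and they make the power conclusion conditional.

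They do not rescue the sentence. Adjustment changes precision, not the size of the outcome SD relative to its mean, so above about 19% zeros 0.25 SD is still not 12%. The authors' calculation also takes no credit for the correlation.

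A second objection is that 12% may be something else under a wrong label. An effect of d = 0.25 converts to r = 0.25/√(0.25² + 4) = 0.124, or to roughly 12 percentage points on a proportion near 50%. Neither document says so. If that is the source, the sentence is still wrong as written, because it refers to volume of offences.

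Third, the harm is limited: results come with confidence intervals, and neither document says that a null result would exclude 12%. That is fair, and it lowers the severity.

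**Conclusion.** The equivalence is unsupported in both documents and, on the plan's own description of who is eligible, implausible. That it requires an SD of 0.48 times the mean and at most about 19% zeros (17.5% to 20.0% with rounding) is arithmetic; it assumes only that 12% means a relative difference in mean volume.

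The size of the consequence depends on an unknown CV. Unless the SD is about half the mean, the 80% power belongs to 0.25 SD and not to 12%. For CVs of 0.75 to 2.0 the detectable difference is 19% to 50%, and unadjusted power for 12% is 44% down to 10%, somewhat higher with baseline adjustment.

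It would be wrong to conclude that the sample size is miscalculated: 506 and 562 are right for d = 0.25. The sentence should be fixed because it is the only offence-scale justification for the target, but sample size, model and endpoint do not change.

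**What to change.** In both documents:

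- Delete the 12% equivalence, or support it with the SRDS mean, SD and zero share from which it was derived.
- State the target as 0.25 SD.
- Report the percentage that 0.25 SD represents, using the pooled, allocation-blind baseline SRDS mean and SD, labelled as baseline values and computed on the scoring used for the primary outcome.
- Say that a null result will be interpreted from the confidence interval, and not as excluding a 12% reduction.

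The 25% to 50% that corresponds to CVs of 1 to 2 should not be written in as the trial's detectable difference; those CVs are assumptions made here to show sensitivity.

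The cost is a few sentences and one blinded summary of data already being collected. The likely downside is that the stated detectable percentage becomes less favourable.

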**Table 2: Sample size calculations**

		PARAMETER
Minimum Detectable Effect Size (MDES)		0.25
Pre-test/ post-test correlations	level 1 (participant)	n/a
	level 2 (cluster)	n/a
Intracluster correlations (ICCs)	level 1 (participant)	n/a

		PARAMETER
	level 2 (cluster)	n/a
Alpha 		0.05
Power		0.8
One-sided or two-sided?		Two-sided
Average cluster size (if clustered)		n/a
Number of clusters 	Intervention	n/a
	Control	n/a
	Total	n/a
Number of participants	Intervention	253
	Control	253
	Total	506 (562 allowing loss at month 6 of 10%)

## Outcome measures

To ensure outcomes are accessible to a wide range of potential participants we will make outcomes available in English and Welsh and provide translators for other languages. As we anticipate a higher level of intellectual disability than the general population, we will seek the advice of specialists in how outcomes can be presented to meet the needs of the target population; this will include using different fonts, colours, and the restriction on the amount

---

 Please adjust as necessary for trials with multiple primary outcomes, 3-arm trials, etc., when a Bonferroni correction is used to account for family-wise errors.

 Please state how the data is clustered, if there is any clustering (e.g., by delivery practitioner or setting).

of text presented on each page. All outcome tools will be agreed with our youth advisory panel prior to use.

### **Baseline measures**

Key demographic variables will be collected at baseline, these include age, sex, ethnicity, and index of material deprivation (IMD) derived from the participants postcode and converted to IMD using the IMD Wales lookup tool:

<https://geoconvert.ukdataservice.ac.uk/help/faq.html>.

### **Primary outcome**

Self-reported delinquency will be assessed using the Self-Report Delinquency Scale (SRDS; (Smith and McVie, 2003)) over the previous six months. This 19-item questionnaire has established psychometric properties (Fonagy et al., 2018) in this population and has a strong correlation ( $R=0.95$ ) with police charges (McAra and McVie, 2007). This outcome will be assessed at baseline, 6- and 12-months post randomisation. As the funder requires a final report by September 2025, the 6-month post-randomisation time-point will be the primary endpoint.

### **Secondary outcomes**

Emotional symptoms and behavioural difficulties will be assessed using the self-completed Strength and Difficulties questionnaire (SDQ; (Goodman, 1997)). This assesses behaviour across several domains including, conduct, hyperactivity, emotional regulation, peer relationships and prosocial behaviour and allows for the generation of two multi-component outcomes: internalising and externalising behaviours with the latter highly associated with current or future offending behaviour. We will assess total score, domain scores and multi-component scores. The outcome is widely used and has demonstrated excellent validity and moderate reliability in adolescent populations (Goodman, 2001). The SDQ is suitable for completion by those aged 10-17 years and those with mild learning disabilities (Law and Wolpert, 2014)

Wellbeing will be assessed using the Short Warwick-Edinburgh Mental Well-being scale (SWEMWBS; (Clarke et al., 2011)). SWEMWBS is a 7-item, self-completed scale addressing different aspects of eudemonic and hedonic mental health wellbeing. The scale is validated for adolescents and demonstrates good internal consistency (Ng Fat et al., 2017), and discriminant, construct and convergent validity (McKay and Andretta, 2017, Ng Fat et al., 2017).

Non-psychotic psychological health will be assessed using the General Health Questionnaire (GHQ12; (Goldberg and Hillier, 1979)), using norms derived for adolescent populations. This

12-item instrument has established validity and reliability in adolescent populations (Baksheev et al., 2011).

To assess the potential impact on the family environment we will assess family cohesion using the Brief Family Relationship Scale (BFRS; (Fok et al., 2014)), this 16-item instrument assesses family relationships, cohesion, and conflict, and has established convergent and discriminant validity.

We will use questions derived from a Client Service Receipt Inventory (CSRI;(Coulton et al., 2022)) to assess the frequency of school attendance, exclusions and suspensions, work status and criminal justice involvement over the previous 6-months. Client Service Receipt Inventory methods are an established and valid form of assessing participant resource use in randomised controlled trials and can be adapted for the target population (Knapp and Beecham, 1990).

All these outcomes will be assessed at baseline and then again at 6- and 12-month post-randomisation.

The assessment battery takes 15 minutes to complete on average based on the use of a similar question battery with an adolescent population in other studies. Each young person will be supported during completion, at baseline by staff in the services and at 6- and 12-month by researchers who will be blind to participant allocation. Research staff will provide training in baseline data collection to staff in Bridgend across the five services through an interactive in-person training session and this will include a training manual and on-going support. At the end of each assessment point and at the end of any qualitative interview the young person will be provided with an opportunity to debrief and reflect on the impact of answering the questions. This debrief is designed to identify any negative impacts of reflecting on themselves and any potential re-traumatisation. If issues are identified, the potential adverse event standard operating procedure will be activated, and trauma leads in each service asked to conduct an assessment and provide any necessary intervention. All adverse events in both arms of the study will be recorded and reported.

In addition to key demographics (age, sex, ethnicity, and IMD) that will be assessed at baseline we will assess the exposure to adverse child experiences assessed on entry to the service using existing records.

Six months after randomisation, in both arms of the study, young people will be contacted by phone or email by researchers and asked to complete the short revised therapeutic alliance scale for children (TASC-r; (Shirk and Saiz, 1992)), this assesses the quality of the relationship between the young person and staff member. Therapeutic alliance is a strong predictor of outcome, and this will be used in the prognostic model (objective 5).

Staff will be asked to complete the Attitudes Related to Trauma Informed Care (ARTIC; (Baker et al., 2016)), a psychometrically robust instrument that assesses professional attitudes and perceptions of trauma informed care. The instrument has established internal consistency (Cronbach  $\alpha$  0.91), test-retest reliability (0.84), criterion and construct validity (Baker et al., 2016). Staff wellbeing will be assessed using the Short Warwick-Edinburgh Mental Well-being scale (SWEMWBS; (Clarke et al., 2011)). They will complete these just prior to randomisation and again 6- and 12-months after randomisation to RBT or BAU. In addition to self-completed outcomes, staff turnover and percent days absent will be assessed over the intervention delivery period from Bridgend administration databases.

### **Compliance**

As interventions are personalised to the young person's needs across both the RBT and BAU groups, compliance and dose will be assessed from two perspectives. From a staff perspective we will assess fidelity to the components of the allocated tier in the RBT arm (case formulation, multi-agency meetings, reviews). For participants, the dose will be assessed in both arms as the proportion of planned meetings attended. Interactions between young people and staff are recorded on the same system between the different participating services. Records include planned meetings, who leads the meeting, staff member, trauma lead or psychologist and attendance. Compliance will be categorised into 5 quintiles, 0-19%, 21-40%, 41-60%, 61-80% and 81-100%. These will be employed in a dose response analysis. In addition, we will use this data to augment the micro-costing of the intervention.

### **Analysis**

The proposed analysis is covered in depth in the associated statistical analysis plan.

Objective 1: Participant flow through the study will be presented as a CONSORT diagram. We will present demographics and outcome variables for each group at each time-point. We will explore the validity of the randomisation procedure by presenting baseline outcomes and estimates of precision by allocated group.

Objective 2: The primary outcome is the mean difference between BAU and RBT in number of offences over the 6 months from baseline, assessed using the SRDS at 6-months. The analysis will be conducted using an analysis by intention to treat (ITT) and will include all available data with participants maintained as members of their allocated group, irrespective of whether they complied with the intervention or not. Data will be assessed for distributional assumptions and will probably take the form of a generalised linear regression model, adjusted for baseline stratification covariates and baseline SRDS score. Both the intervention and control vary by service, with a higher to lower hierarchy of complexity running from youth justice, edge of care, children's services, youth development to early help. What is delivered in both the intervention and control group is tailored to the young person's needs. While we

can describe the variety of different sessions delivered in our results, we cannot completely account for it in the analysis, nor can we adjust for any potential contamination due to multi-agency working. Instead, we take a holistic approach, seeing what is delivered as a whole, rather than the sum of its individual parts. Though as complexity is hierarchical across services, we will adjust the analysis for service. This provides the best estimate of effect of how the intervention is proposed to be implemented across diverse services and as a rigorously designed RCT any potential errors introduced will be equally distributed across both groups and mitigated in the analysis. We will apply a multi-level model allowing for participants to be nested within services as a fixed effect. Results will be presented as a mean difference and associated 95% confidence intervals. A secondary analysis will be conducted using a similar approach at month 12.

Secondary outcomes will be assessed in a similar way by establishing diagnostic plots to identify the most appropriate regression approach; logistic for dichotomous outcomes, ordinal for ordered categorical outcomes, linear for continuous outcomes and fractional for proportions. Stratification factors and baseline covariates will be included within the model.

If the missing data exceeds 5%, sensitivity analyses will be performed using a pattern mixture approach and multiple imputation to compare the sensitivity of conclusions to varying assumptions about the missing data, particularly whether data is missing at random (MAR) or missing not at random (MNAR). This allows for an assessment of both random and systemic bias. Results based on complete data analysis, MAR and MNAR will be presented to explore the influence of missing data on outcomes observed.

We will conduct a Complier Average Causal Effects (CACE) analysis using an instrumental variable framework to explore the impact of compliance on the primary outcomes at different levels of compliance, both fidelity to the steps involved in each tier and quintiles of compliance. CACE weights the analysis by the ITT treatment effect by the proportion of compliance, this allows the estimation of unbiased treatment effects and maintains the allocation in the analysis.

Objective 3: For staff we will explore the differences between the groups in terms of overall wellbeing, perceptions of working in a trauma informed manner and confidence in working with young people who have experienced adverse childhood experiences derived from the SWEMWBS and ARTIC questionnaire at months 6 and 12 using linear regression adjusted for baseline score and service. Staff turnover and proportion absence will be assessed in a similar manner using fractional regression.

Objective 5: Stepwise regression analysis will be performed to model the relationship between pre-randomisation factors and demographics, on observed outcomes at 6 months.

Interaction terms with allocation arm will be included in the analysis, and a significance level of 0.1 will be used to determine which factors are to be included in the regression model. Pre-randomisation factors will include sex, age, ethnicity, IMD, family cohesion, adverse childhood experiences assessed by the service, and process measures, staff perceptions, staff confidence, and therapeutic alliance. The allocated arm will be included in this analysis as an interaction term.

Objective 6: To maintain power in analysis we will avoid the analysis of sub-groups. We will use latent class analysis to explore the existence of subgroups within the sample who may have a differential response to the intervention.

